5. MILESTONES

The initial planned dates for key milestones in this study are outlined below.

Milestone:	Planned Date:
Start of data collection ^a	30/04/2022*
Summary report feasibility assessment 1 ^b	10/11/2022*
Summary report feasibility assessment 2 ^b	Q3 2023
Interim report	No interim report will be generated for this study
Data extraction (querying) for final study report	Q1-Q2 2023
End of data extraction ^c	Q2 2024
Final report of study results to Janssen ^d	Q3 2024

* Actual dates.

^a Start of data collection is the planned date for starting data extraction for the feasibility assessment.

^b Summary reports will be generated according to feasibility assessment.

^c End of data extraction is the planned date the analytical dataset (the minimum set of data required to perform the statistical analyses for the primary objective) is completely available including findings from the case validation process.

^d Final report will be submitted by Janssen to the appropriate health authority agencies as per health authority agreed timelines.

6. BACKGROUND AND RATIONALE

6.1. Background

SARS-CoV-2 Virology and COVID-19 Disease Burden

The severe acute respiratory syndrome coronavirus-2 (SARS-CoV-2) is an enveloped, positive-sense, single-stranded ribonucleic acid (RNA) Beta coronavirus ([Coronaviridae Study Group of the International Committee on Taxonomy of Viruses 2020](#), [Wu 2020](#)). It was first identified following reports of a cluster of acute respiratory illness cases in Wuhan, Hubei Province, China in December 2019 ([Li Q 2020](#)). Early epidemiological investigations suggested that the majority of early cases were linked to a food market, with patients infected through zoonotic or environmental exposure, followed by the subsequent spread of infection by human-to-human transmission among close contacts ([Li Q 2020](#)). However, there is some controversy about the initial origin of the virus ([Cyranoski 2020](#)). Genomic sequencing was performed on bronchoalveolar lavage fluid samples collected from patients with viral pneumonia admitted to hospitals in Wuhan, which identified a novel RNA virus from the family Coronaviridae ([Lu 2020](#), [Wu 2020](#)). Phylogenetic analysis of the complete viral genome revealed that the virus, SARS-CoV-2, is part of the subgenus Sarbecovirus of the genus Betacoronavirus, and is most closely related (approximately 88% identity) to a group of severe acute respiratory syndrome (SARS)-like coronaviruses previously sampled from bats in China ([Lu 2020](#)).

As of 26 August 2021, approximately 212,418,6624 cases and 4,436,327 deaths from Coronavirus Disease 2019 (COVID-19) have been reported worldwide. Approximately 36,307,572 cases including 750,921 deaths have been reported in the EU/European Economic Area ([ECDC 2020](#)). In the United States (US) approximately 39,210,669 cases and 640,223 deaths have been reported ([Johns Hopkins CSSE 2020](#)). India is the South Asian country that has been affected the most by COVID-19. The country has reported more than 32.8 million cases and the death toll has passed 1 million. In April 2021 alone, India added almost six million new cases partly caused by the new Covid-19 variant, identified as B.1.617 ([Yadav 2021](#)). South Africa is the African country that has been affected the most by COVID-19 with 2,777,659 cases and 82,261 deaths reported ([Johns Hopkins CSSE 2020](#)).

Ad26.COVS2.S Vaccine

Ad26.COVS2.S (also known as Ad26COVS1, VAC31518, JNJ-78436735) is a monovalent vaccine composed of a recombinant, replication-incompetent adenovirus type 26 (Ad26) vector, constructed to encode the SARS-CoV-2 Spike (S) protein, stabilized in its prefusion conformation.

The S protein is the major surface protein of coronaviruses. Different animal models have been used for the evaluation of candidate vaccines against SARS-CoV, and the common conclusion that has emerged is that the viral S protein is the only significant target for neutralizing antibodies ([Buchholz 2004](#), [Sui 2005](#), [Zhang 2004](#), [Zhou 2004](#)) and the only viral protein that can elicit protective immunity in animal models ([Berry 2004](#), [Bisht 2004](#), [Bukreyev 2004](#), [Subbarao 2004](#)).

Ad26.COV2.S encodes a membrane-bound full-length S protein derived from a SARS-CoV-2 clinical isolate ([Wuhan 2019](#), whole genome sequence NC_045512), with 2 amino acid changes in the S1/S2 junction that knock out the furin cleavage site, and 2 proline substitutions in the hinge region.

At the time of the primary analysis of Phase 3 study VAC31518COV3001 (data lock point 22 January 2021) safety analysis of Ad26.COV2.S demonstrated that the vaccine has an acceptable safety and reactogenicity profile when administered as a single dose or as a 2-dose regimen at dose levels up to 1×10^{11} viral particles (vp) in adults at 18 years of age or above, including adults at 60 years of age or above. There was a trend towards a decrease in the frequency of solicited local and systemic adverse events (reactogenicity) with a decreasing dose level of Ad26.COV2.S (from 1×10^{11} vp to 2.5×10^{10} vp). Reactogenicity was demonstrated to be transient and most solicited adverse events (AEs), including pyrexia, generally resolved in 1 to 2 days post-vaccination. No significant safety issues were identified. However, a numerical imbalance was observed for venous thromboembolism (VTE). In general, a lower reactogenicity profile was observed in older adults compared with younger adults ([data on file](#)).

On 27 February 2021, the US Food and Drug Administration (FDA) granted an emergency use authorisation (EUA) for the Ad26.COV2.S vaccine for use in individuals 18 years of age and older ([FDA 2021](#)). On 11 March 2021, European Medicines Agency (EMA) granted a conditional marketing authorisation (cMA) for Ad26.COV2.S for use in individuals 18 years of age and older ([EMA 2021](#)). The UK Medicines and Healthcare products Regulatory Agency (MHRA) granted a cMA on 28 May 2021 ([MHRA 2021](#)).

As of 12 April 2021, more than 6.8 million doses of the Ad26.COV2.S vaccine have been administered in the US. Up to that date, 6 cases of cerebral venous sinus thrombosis (CVST) along with low platelet counts were reported ([Cines 2021](#)). In response to these cases, the US FDA and the Centers for Disease Control and Prevention (CDC) recommended a pause in the use of the Ad26.COV2.S vaccine in the US on 13 April 2021, to allow for further investigations on these rare events of thrombosis with thrombocytopenia. Similar cases of thrombosis with thrombocytopenia had also been reported in individuals who received the Vaxzervria/COVID-19 AstraZeneca Vaccine outside the US ([Greinacher 2021](#), [Schultz 2021](#), [Scully 2021](#)). This syndrome has been termed “vaccine-induced prothrombotic immune thrombocytopenia (VIPIT)” or “vaccine-induced immune thrombotic thrombocytopenia (VITT)” but is now named “thrombosis with thrombocytopenia syndrome (TTS)”. This rare and new syndrome is characterised by thrombosis (such as CVST or splanchnic thrombosis), thrombocytopenia and confirmed with a positive platelet factor 4 (PF4)-heparin enzyme-linked immunosorbent assay. There is currently no standard case definition for TTS accepted for use by all countries. In this regard, the Brighton Collaboration developed an interim case definition of TTS ([Brighton Collaboration 2021](#)). VAC4EU organised a webinar to discuss the operationalisation of this event, for which background rates were generated for EMA ([Willame 2021](#)). In addition, the PRAC’s recommendation for the categorisation of TTS will be taken into account.

In response to the pausing in administration of Ad26.COVS.2 in the US, 2 emergency Advisory Committee on Immunization Practices (ACIP) meetings were convened to review these reported cases and to consider potential implications on the Ad26.COVS.2 vaccination policy. Meanwhile, a series of 12 cases of CVST combined with low platelet counts, were identified through the Vaccine Adverse Event Reporting System in the US (Karron 2021). On 23 April 2021, ACIP concluded that the benefits of resuming Ad26.COVS.2 vaccination among individuals aged ≥ 18 years outweighed the risks and reaffirmed its interim recommendation under FDA's EUA. The sponsor was requested to revise the Ad26.COVS.2 vaccine fact sheet to include a warning for rare clotting events among women aged 18 to 49 years.

Similarly, the EMA Pharmacovigilance Risk Assessment Committee (PRAC) assessed cases of thrombosis after vaccination with Ad26.COVS.2 vaccine. On 20 April 2021, the PRAC confirmed that the available data show that the Ad26.COVS.2 vaccine's known and potential benefits outweigh its known and potential risks in individuals 18 years of age and older. The sponsor was asked to update the Summary of Product Characteristics (SmPC) and Package Leaflet to include important information on the diagnosis and management of TTS. On 6 May 2021, the PRAC recommended to further updating the SmPC and European Union (EU) Risk Management Plan including the addition of TTS as an important identified risk. Thromboembolism should be maintained as an important potential risk. In addition, EMA recommends that PASS should include adverse events of special interest (AESIs) of concern. The Brighton Collaboration Interim Case Definition for TTS should also be considered for case findings.

On 18 June 2021, an Emerging Safety Issue (ESI) notification was sent to EMA regarding an internally identified significant safety issue around cases of Capillary Leak Syndrome (CLS) reported with Ad26.CoV2.S.

- Following the AESI notification to EMA a Type 2 variation was submitted on 25 June 2021 to update the European Union Product Information (EUPI) with a contraindication for individuals who have previously experienced episodes of CLS. In addition, an updated direct healthcare professional communication to inform healthcare professionals of the contraindication for individuals who have previously experienced episodes of CLS was submitted to EMA on 25 June 2021. Upon EMA request wording related to CLS was also added to sections 4.4 and 4.8 of the EUPI. This variation was approved on 09 July 2021.
- In the US Janssen notified the FDA of the internally identified significant safety issue around cases of CLS reported with Ad26.CoV2.S. also on 18 June 2021 and submitted as per guidance obtained from the FDA a Clinical Overview which included an executive summary for CLS and a cumulative review that includes supportive data, narratives and Council for International Organizations of Medical Sciences on 25 June 2021.

On 7 July 2021, based on an FDA review of cases of Guillain-Barré syndrome (GBS) reported in recipients of the Janssen COVID-19 Vaccine, FDA required updates to the product label to include a warning statement and associated information regarding GBS following vaccination. Janssen agreed to consider GBS a significant safety issue. In addition, FDA provided comments regarding their review of capillary leak syndrome (CLS). FDA did not conclude that in individuals with a history of CLS, the risk of receiving the Janssen COVID-19 vaccine clearly outweighs any possible

benefit and the agency believes it is appropriate to include CLS in Section 6.2 Post Authorisation Experience of the Fact Sheet for Healthcare Providers Administering Vaccine (Vaccination Providers). On 8 July 2021, Janssen submitted updated factsheets to the EUA accepting the FDA positions on GBS and CLS. Approval was received on 12 July 2021.

On 12 July 2021, a type II variation was submitted to EMA to update the EUPI to include GBS as an Adverse Drug Reaction (ADR) in section 4.8 and to include related wording in Section 4.4 of the EUPI.

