 - thrombotic events (microangiopathy including capillary leak syndrome), disseminated intravascular coagulation, deep vein thrombosis, pulmonary embolism, cerebral vein thrombosis, peripheral thrombosis, thrombosis with thrombocytopenia and ischemic strokes, acute coronary syndrome (acute myocardial infarction, unstable angina, and new onset angina),
 - bleeding events including haemorrhagic stroke (no subarachnoid),
 - composite endpoint: Venous thrombosis (including pulmonary embolism and deep vein thrombosis)
 - composite endpoint: Arterial thrombosis (including acute coronary syndrome and ischemic stroke),
 - composite endpoint: stroke (including haemorrhagic and non-hemorrhagic stroke)
 - heart failure, and stress cardiomyopathy.
- The incidence of immune/inflammatory events: encephalitis (including acute demyelinating encephalomyelopathy and meningoencephalitis), Guillain-Barré Syndrome, Bell's palsy, immune thrombocytopenia, thrombocytopenia, transverse myelitis and cardiac inflammatory disorders (including myocarditis and pericarditis) within 1-42 days.
- The incidence of sensorineural hearing loss within 1-60 days.
- The incidence of asthma exacerbation within 1-14 days.

Non-acute events (events expected to be recorded >60 days after vaccination)

- The incidence of new-onset autoimmune thyroiditis, multiple sclerosis, acute aseptic arthritis, and type 1 diabetes mellitus within 1-365 days.

Newly identified AESI may be incorporated into the list of AESI to be investigated by the current study if a safety signal occurs.

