8.1.2. Overview of Study Design for Safety Evaluation Study

Evaluation of safety concerns will be conducted using a retrospective observational study in electronic health care databases of various types in Europe. Eligible individuals will be included in the study from the start of Ad26.COV2.S vaccination in each participating country, and the study will end at the last date of data availability in each database.

For each AESI, the study design of the safety evaluation study will depend on whether the AESI is an acute or non-acute event and follow the decision framework described in the ACCESS template protocols for evaluation of safety events in electronic health care databases ([Dodd 2020](#)).

The primary study design for the evaluation of acute events (events expected to occur within 2, 14, 28, 42, or 60 days of vaccination) will be a self-controlled risk interval (SCRI) design with pre- and post-vaccination control window and for non-acute events (events expected to occur within 365 days) will be a cohort design with concurrent unexposed comparators. Additionally, the cohort analysis will also include two active comparator groups: one viral vector vaccine comparator group (i.e., Vaxzevria[®] [AZD1222] by Oxford/AstraZeneca) and one mRNA vaccine comparator group (i.e., Comirnaty[®] [tozinameran] by Pfizer/BioNTech and/or Spikevax[®] [elasomeran] by Moderna), where possible (pending on the feasibility analysis with a maximum follow-up time of one year).

In sensitivity analyses, an equivalent cohort design will also be used to assess acute events. When it is established that data sources do not capture vaccinations well during the feasibility assessment, we will conduct a sensitivity analysis excluding these data sources from the cohort analysis with non-exposed comparators for the non-acute events, to avoid misclassification of exposure.

Another sensitivity analysis will compare the Ad26.COV2.S vaccine with active comparators (1) a 1-dose strategy and (2) a 2-dose strategy.

Individuals start follow-up at the start of each risk window and end follow-up at the earliest occurrence of latest data availability of the databank, individual exit from the database, completion of the study period, or death. At least one year of enrolment prior to the index date (date of vaccination) will be required to determine whether individuals meet the study criteria and to define baseline characteristics. If more historical data is available, this will be included.

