[Figure 1](#) shows the SCRI study design diagrammatically using an example with a risk window and control window of 42 days.

Figure 1: Self-Controlled Risk Interval Design

T is time and T=0 is the index date.

8.1.2.2. Cohort Design (Primary Study Design for Non-acute Events and Sensitivity Analysis Design for Acute Events)

For the primary analysis of non-acute events, a retrospective cohort design will be used to estimate the rate of vaccination with Ad26.COV2.S vaccine, describe the characteristics of these vaccinated individuals and subsequently to estimate the incidence of new-onset autoimmune thyroiditis, multiple sclerosis, acute aseptic arthritis, and type 1 diabetes mellitus after receipt of the vaccine dose and to compare this incidence with that occurring in an unvaccinated matched comparator group, and in two groups of individuals exposed to other types of COVID-19 vaccines (i.e., one viral vector vaccine comparator group vaccinated [i.e., Vaxzevria[®] {AZD1222}] by Oxford/AstraZeneca) and one mRNA vaccine comparator group (i.e., Comirnaty[®] [tozinameran] by Pfizer/BioNTech and Spikevax[®] [elasomeran] by Moderna).

As a sensitivity analysis for acute events, a cohort analysis (following the same approach used in the main analysis for non-acute events) will be conducted.

- **Exposed cohort:** individuals will have received at least 1 dose of Ad26.COV2.S vaccine.
- **Concurrent unexposed cohort:** individuals that have not been vaccinated with Ad26.COV2.S vaccine or any other COVID-19 vaccine at any time prior to the index date (time zero) matched to the vaccinated individual for important characteristics as described in Section 8.7.2.1.
- **Cohort exposed to other COVID-19 vaccines:** individuals will have received at least 1 dose of a viral vector COVID-19 vaccine (i.e., Vaxzevria[®] [AZD1222] by Oxford/AstraZeneca) or an mRNA COVID-19 vaccine (Comirnaty[®] [tozinameran] by Pfizer/BioNTech and Spikevax[®] [elasomeran] by Moderna, respectively).

A sensitivity analysis will compare the Ad26.COV2.S vaccine with the active comparators with 1) a 1-dose strategy and 2) a 2-dose strategy.

In this retrospective cohort design, the start of follow-up will be defined as the time when study outcomes start to be counted. The index date in the exposed cohorts (i.e., recipients of the vaccines)

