8.2.5. Exclusion Criteria

For the feasibility assessment, there will be no exclusion criteria.

Individuals will be excluded from the safety evaluation study if:

- They have been vaccinated with any other COVID-19 vaccines before starting each risk window.

- Record of the specific AESI during the specific corresponding washout periods for the SCRI and cohort analyses. Individuals with such acute diagnoses before the AESI-specific washout periods will not be excluded. For clarification, when one AESI will be investigated, any history or prevalence of other AESIs will not be excluded. [Table 1](#) shows the specific washout periods for each AESI.

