8.3.3. Evaluation of Safety Outcomes

The sponsor has created a list of AESIs based on current knowledge of the Ad26.COV2.S vaccine. [Table 1](#) lists and explains the AESIs to be ascertained in the study with specific risk windows. Background incidence rates for most of the data sources and AESIs are available on the VAC4EU dashboard <https://vac4eu.org/covid-19-tool/>. Definitions and codes are available on Zenodo (<https://zenodo.org/communities/vac4eu/>).

Table 1: AESI-Specific Risk Windows and Washout Periods for Patient Inclusion in the Study

Body System	AESI	Disease-specific washout period before the index date	Disease-specific risk window following the index date
Nervous and central nervous system	Encephalitis, including ADEM and meningoencephalitis	365 days	1-42 days
	Guillain-Barré Syndrome	365 days	1-42 days
	Transverse myelitis	365 days	1-42 days
	Bell's palsy	365 days	1-42 days
	Multiple sclerosis, including optic neuritis	365 days	1-365 days
	Sensorineural Hearing loss	365 days	1-60 days
	Generalised convulsion	365 days (w/o epilepsy) 90 days (w/o non-epileptic seizures)	1-14 days
Immune system	Autoimmune thyroiditis	365 days	1-365 days
	Immune thrombocytopenia	365 days	1-42 days
	Type 1 diabetes mellitus	Any time prior*	1-365 days
	Acute aseptic arthritis	365 days	1-365 days
	Anaphylaxis	90 days	0-2 days
Cardiac system	Cardiac inflammatory disorders, including myocarditis and pericarditis	365 days	1-28 days
	Microangiopathy	365 days	1-28 days
	Heart failure	365 days	1-28 days
	Stress cardiomyopathy	365 days	1-28 days
	Coronary artery disease, including acute myocardial infarction	365 days	1-28 days
	Arrhythmia	365 days	1-14 days
Blood and lymphatic system disorders	Deep vein thrombosis	365 days	1-28 days
	Pulmonary embolism	365 days	1-28 days
	Disseminated intravascular coagulation	365 days	1-28 days
	Non-haemorrhagic stroke	365 days	1-28 days
	Haemorrhagic Stroke	365 days	1-28 days
	thrombocytopenia	365 days	1-28 days
	peripheral thrombosis	365 days	1-28 days
	Sinus thrombosis	365 days	1-28 days
	Thrombotic Thrombocytopenia syndrome	365 days	1-28 days
	Composite: venous thrombosis	365 days	1-28 days
	Composite: arterial thrombosis	365 days	1-28 days
Composite: strokes	365 days	1-28 days	
Renal system	Acute kidney failure	365 days	1-14 days
Hepatic system	Acute hepatic failure	365 days	1-14 days
Respiratory system	Exacerbation of asthma	365 days	1-14 days

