As of 08 May 2021, ~65,000 doses of Ad26.COV2.S vaccine have been administered in the Netherlands. Assuming PHARMO covers ~20% of the Dutch population, this should be 16,250 doses in PHARMO's catchment area. However, different healthcare providers administer the COVID-19 vaccines (i.e., GPs, the public health service and healthcare institutions) in the Netherlands. The vaccination data are recorded in a central register (if people have given permission beforehand), the COVID-19 vaccination Information and Monitoring System. PHARMO is currently exploring the possibilities to link with this register. Until then, the GP Database will be the basis for the vaccination data. The GP Database contains vaccinations administered by GPs and by the public health service, as GPs receive an automated notification when a patient has a positive corona test or has been vaccinated via the public health service (as long as people have given their consent).

It is difficult to estimate how many persons will be vaccinated with Ad26.COV2.S vaccine during the study period in the Netherlands. The Dutch government wants everyone from the age of 18 to have had at least one dose of COVID-19 vaccine by the beginning of July 2021. This vaccination schedule depends on many factors (e.g., approval and effectiveness, delivery and distribution of vaccines to injection sites, such as hospitals and GPs, new developments and advice from, for instance, the Health Council of the Netherlands (i.e., de Gezondheidsraad). Also, the choice of the type of vaccination depends on different factors, such as type of work (care workers), home living (yes or no), year of birth and existing comorbidities. PHARMO acknowledges that the data source they have access to includes data on vaccine delivery and registration and undertakes to cooperate in addressing the Study objectives by contributing to providing reports based on such data.

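### In the cohort sensitivity analysis of microangiopathy (including capillary leak syndrome), people with older CLS stay eligible as unexposed comparators although the EU label came to contraindicate Ad26.COV2.S for them, which can attenuate the rate ratio

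*Protocol*

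**What the plan says.** - **Label.** Section 6.1 describes an EU variation submitted on 25 June 2021 to update the product information "with a contraindication for individuals who have previously experienced episodes of CLS". It then states: "This variation was approved on 09 July 2021".
- **Outcome.** Section 7 lists CLS inside a wider acute endpoint: "thrombotic events (microangiopathy including capillary leak syndrome". Table 1 (section 8.3.3) has no CLS row. The row that covers it reads "Microangiopathy 365 days 1-28 days", that is, a 365-day washout and a risk window of days 1 to 28.
- **Older history.** Section 8.2.5 states: "Individuals with such acute diagnoses before the AESI-specific washout periods will not be excluded". None of the exclusion criteria refers to the contraindication.
- **Design.** Acute events are analysed primarily by the self-controlled risk interval (SCRI) design in Ad26.COV2.S recipients. Section 8.1.2.2 adds: "As a sensitivity analysis for acute events, a cohort analysis (following the same approach used in the main analysis for non-acute events) will be conducted". Comparators are unexposed people and recipients of other COVID-19 vaccines, matched 1:1.
- **Confounder control.** The matching list in section 8.7.2.1 covers age, sex, pregnancy, immunocompromised state, prior COVID-19, calendar time and risk factors for severe COVID-19. The comorbidity list in section 8.3.4 does not name CLS history.
- **Accrual.** Section 8.1.2 states: "Eligible individuals will be included in the study from the start of Ad26.COV2.S vaccination in each participating country". Section 8.4.3 shows use before the label change: "As of 08 May 2021, ~65,000 doses of Ad26.COV2.S vaccine have been administered in the Netherlands".

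**The concern.** The exposed and unexposed arms of the cohort analysis do not draw on the same people. After 09 July 2021 someone with CLS two years earlier was, under the label, not a candidate for Ad26.COV2.S. The same person can still be drawn as an unexposed comparator, because the washout looks back only 365 days. If earlier CLS raises the rate of further CLS, the comparator arm carries recurrences that the exposed arm largely lacks. This is confounding by contraindication, and it lowers the rate ratio.

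The cohort analysis is there to check the SCRI. Section 8.1.3 gives the SCRI's lower power and its exposure to time-varying confounding as the reasons for adding it. A ratio biased towards no effect would weaken that check for a risk that the sponsor itself notified to the regulator.

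**Working it through.** **The plan's own figures.** No figure is disputed. Table 2 follows from n = 2(z₀.₉₇₅ + z₀.₈₀)² / ln(U)² / (IR × 60/365). For U = 3 and IR = 100 per 100,000 person-years (PY), this is 2 × 7.849 / 1.2069 / 0.00016438 = 79,121, as printed. All 16 cells agree to within one subject.

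**Bias model.** Let b be the microangiopathy rate in people without earlier CLS, p the prevalence of CLS older than 365 days, r the recurrence rate in those people, and e the fraction of them still present in the exposed arm. Assume one true rate ratio for first and recurrent events. Then

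observed IRR / true IRR = (b + e·p·r) / (b + p·r).

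The factor is below 1 whenever e < 1 and p·r > 0.

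**Inputs.** The protocol gives no CLS rate, history prevalence or recurrence rate, so these are assumptions: b = 0.1, 1 or 10 per 100,000 PY; p = 10⁻⁷ to 10⁻⁵; r = 0.1 to 1 per year. The product p·r then runs from 0.001 to 1 per 100,000 PY. Setting e = 0 means that nobody with earlier CLS was vaccinated. Setting e = 0.5 allows for vaccination before the label change or despite it.

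| b per 100,000 PY | e = 0, smallest p·r | e = 0, largest p·r | e = 0.5, largest p·r |
|---|---|---|---|
| 10 | 10/10.001 = 1.00 | 10/11 = 0.91 | 10.5/11 = 0.955 |
| 1 | 1/1.001 = 0.999 | 1/2 = 0.50 | 1.5/2 = 0.75 |
| 0.1 | 0.1/0.101 = 0.99 | 0.1/1.1 = 0.09 | 0.6/1.1 = 0.545 |

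Two benchmarks at e = 0 do not depend on these ranges. If p·r is at most 1% of b, the factor is at least 1/1.01 = 0.99. If p·r equals b, it is 0.50, and a true ratio of 2 reads as 1.0.

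**Expected counts.** Events over the 28-day window = N × 28/365.25 × rate.

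- At the minimum target of 100,000 (section 8.5.1), first cases are 0.008, 0.08 and 0.8 at the three values of b. Comparator recurrences are below 0.08.
- At 1.81 million (the 10% ceiling on 18.1 million, section 8.5), first cases are 0.14, 1.4 and 14. Recurrences are about 0.001 to 1.4.
- The 18.1 million includes 3.6 million from ARS Toscana, which cannot currently contribute. Ten per cent of the remaining 14.5 million is 1.45 million, giving first cases of 0.11, 1.1 and 11.

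Within the assumed range p·r never exceeds 1 per 100,000 PY, so recurrences match or outnumber first cases only when b is about 1 or lower. At b = p·r = 1, the comparator arm of 1.81 million expects 1.81 million × 28/365.25 × 2/100,000 = 2.8 events.

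Table 2 leads to the same place. At 1 per 100,000 PY it needs 1,801,142 exposed for an upper limit of 10 over 60 days. Over 28 days that becomes 1,801,142 × 60/28 = 3.86 million, more than the ceiling.

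**The case against.** The strongest reply is that this is a sensitivity analysis of a pooled outcome with very few events. The SCRI has no comparator cohort and is untouched. Other microangiopathy events dilute any CLS recurrences. Where recurrences could matter proportionally, imprecision already dominates. All of this stands, and it caps the importance of the point.

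It can also be said that keeping older history is deliberate. Section 8.2.5 states it outright, and section 8.7.3 makes people with the event more than a year earlier a secondary subpopulation. That subgroup, however, is run within the primary design, which for an acute event is the SCRI, so it does not clean the cohort estimate.

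Section 8.7.1.2 provides for adjustment when other covariates prove associated with exposure and outcome, section 8.3.4 allows outcome-specific covariate sets, and the SAP may say more. This safeguard is real but weak here, since a history this rare is unlikely to show up as an imbalance.

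A reader might go further on two counts. One is that the comparisons with other vaccines are biased in the same way. The protocol does not say whether those vaccines carried a similar restriction, so this cannot be settled. The other is that people with earlier CLS were barred from Ad26.COV2.S throughout. Inclusion starts at national roll-out and the contraindication came later, so the imbalance is only partial.

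**Conclusion.** The point holds for one analysis: the cohort comparison of microangiopathy, including CLS, between Ad26.COV2.S recipients and unexposed people. The direction is downward, provided that earlier CLS raises the rate of later CLS and that the label was followed at least in part.

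The size cannot be fixed from the protocol. The effect is negligible if recurrences are a small share of microangiopathy events. It is large only if they rival first cases, and there the expected counts are too low for a precise estimate. The factors in the table rest wholly on assumed rates and should not be cited as estimates of the bias.

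It would be tempting to conclude that the study will hide a CLS risk. The documents do not support that: the primary estimate for this outcome comes from the SCRI, and no separate CLS rate ratio is specified. This is a cheap improvement of low importance.

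**What to change.** In Table 1 and section 8.2.5, for the cohort analysis of microangiopathy/CLS only, exclude anyone with a CLS record at any time before index from every arm: Ad26.COV2.S, unexposed, viral vector and mRNA. Report the 365-day version beside it. Leave the SCRI and the prior-history subgroup unchanged. Table 1 already uses an any-time-prior washout for type 1 diabetes, so the device is not new to this protocol.

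The cost is a table footnote, a CLS code subset within the microangiopathy definition, and one extra run. With p·r removed from both arms the model factor becomes 1.00, but only for recorded history. Entry requires just 12 months of prior data, so some older CLS will remain unseen.

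The downside is that the restricted estimate applies to people without CLS history and drops anyone with earlier CLS who was vaccinated before the contraindication. That is the reason to show both versions.
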